With two enrollment periods of 19 months each and assuming an event rate of 3.5% per annum for MACE, a total of approximately 8000 subjects (about 4000 per enrollment cohort) randomized in a 1:1:1 ratio to ertugliflozin 5 mg, ertugliflozin 15 mg or placebo will be sufficient to accrue approximately 714 MACE events within approximately 5.0 years and approximately 939 MACE events within approximately 6.1 years from the start of this study. These calculations assume that subjects will withdraw from the study at a rate of 5% per annum.

Power for Secondary Hypotheses

For the Stage 2 analyses of secondary endpoints, using an O'Brien-Fleming alpha-spending approach and assuming accrual of at least 442 and 582 composite events of cardiovascular death or hospitalization for heart failure at the interim and final analysis respectively, the study will have approximately 90% power to demonstrate superiority of ertugliflozin to placebo on the composite of cardiovascular death or hospitalization for heart failure when the true HR=0.75. Moreover, assuming accrual of at least 287 and 377 cardiovascular death

events at the interim and final analysis respectively, the study will have approximately 83% power to demonstrate superiority of ertugliflozin to placebo on cardiovascular death when the true HR=0.725. With accrual of at least 144 and 190 renal composite events at the interim and final analysis respectively, the study will have approximately 79% power to demonstrate superiority of ertugliflozin to placebo on the renal composite endpoint when the true HR=0.65.

9.1.1. Sample Size for Insulin with or without Metformin Add-on Glycemic Sub-Study:

The sub-study is powered to demonstrate superiority of ertugliflozin compared with placebo in reducing HbA1c from Baseline to Week 18. It is estimated that a minimum of 450 subjects will be enrolled into the sub-study. The sub-study enrollment will not be allowed to exceed 50% of the overall trial sample size. The final determination of inclusion in the sub-study will be based on a programmatic assessment of the sub-study criteria.

In two recent studies of another SGLT2 inhibitor (dapagliflozin) in subjects with type 2 diabetes receiving high doses of insulin, estimates of the standard deviation of the change from baseline in HbA1c after 24 weeks ranged up to a maximum of 0.98%.^{15,16} Therefore, a standard deviation of 1.0% was taken as a conservative estimate for sample size calculations.

Assuming a standard deviation of 1.0% and a lost to follow up rate of 10%, a sample size of 450 subjects (150 per arm) will provide approximately 98% power to detect a difference of 0.5% in the reduction of HbA1c from Baseline to Week 18 between ertugliflozin and placebo using a 2-sided 0.05 alpha level test.

9.1.2. Sample Size for SU Monotherapy Add-on Glycemic Sub-Study:

The primary endpoint for the sub-study is the HbA1c change from Baseline to Week 18. It is estimated that approximately 170 subjects will be enrolled into the sub-study. The final determination of inclusion in the sub-study will be based on a programmatic assessment of the sub-study criteria.

Assuming a standard deviation of 1.0%, a lost to follow up rate of 10%, and a sample size of 170 subjects (~56 per arm), the power to detect a between treatment difference of 0.6% will be approximately 85% using a 2-sided alpha level of 0.05.

9.1.3. Sample Size for Metformin with SU Add-on Glycemic Sub-Study

The primary endpoint for this sub-study is the HbA1c change from Baseline to Week 18. It is estimated that at least 260 subjects will satisfy the criteria for inclusion in this sub-study. Assuming a standard deviation of 1.0% and a lost to follow up rate of 10%, a sample size of 260 subjects (~86 per arm) will provide approximately 96% power to detect a difference of 0.6% in the reduction of HbA1c from Baseline to Week 18 between ertugliflozin and placebo using a 2-sided 0.05 alpha level test.

As there is no separate randomization stratum for the metformin with SU sub-study, this sub-study will consist of a sub-group of subjects from the “main cardiovascular study”

stratum. The determination of inclusion in the sub-study will be based on a programmatic assessment of the sub-study criteria; see [Section 3.4](#).

9.2. Primary Cardiovascular Endpoints Analysis

The two doses of ertugliflozin will be pooled for the analysis of cardiovascular endpoints. The analyses described below will be performed at the interim analysis and at the end of the trial.

The Stage 1 meta-analysis population will include all randomized subjects who have taken at least one dose of investigational product across the Phase 2 and 3 development program. The Stage 2 non-inferiority analysis population will include all randomized subjects who have taken at least one dose of investigational product in this study. For both stages, subjects will be analyzed in the group to which they were assigned by IVRS, regardless of the actual treatment received and only events confirmed by the Endpoint Adjudication Committee will be included in the analysis. For Stage 1, all confirmed MACE plus events will be included in the primary analysis. For Stage 2, confirmed MACE events occurring between randomization and 365 days after the last dose of study treatment will be included in the primary non-inferiority analysis.

The MACE plus and MACE endpoints will be analyzed using a stratified Cox proportional hazards model including treatment group as a covariate. For the Stage 1 meta-analyses, the Cox model will include “Study” as a stratification factor with the following three levels: cardiovascular study, placebo-controlled non-cardiovascular studies, and active-controlled non-cardiovascular studies. For the Stage 2 analyses, the Cox model will include “Cohort” as the stratification factor with the following levels: Cohort 1 (subjects randomized between December 2013 and July 2015) and Cohort 2 (subjects randomized in 2016 and beyond). A test of non-inferiority at the one-sided 0.025 significance level will be performed based on the Cox model. The upper bound of the alpha-adjusted two-sided confidence interval (CI) for the hazard ratio (HR) (ertugliflozin to a non ertugliflozin comparator group or placebo) will be calculated using an O’Brien-Fleming alpha spending function and compared with the appropriate non-inferiority margin (1.8 or 1.3).

Kaplan-Meier curves for the distribution of time to MACE and MACE plus will also be provided for each of the three treatment groups.

Subjects without cardiovascular events will be censored at the earliest of the study cut-off date, last contact date, or end of the applicable analysis ascertainment window (eg, 365 days after the last dose for primary Stage 2 non-inferiority analyses).

9.3. Secondary Endpoints Analysis

Secondary time-to-event endpoints (eg, fatal and non-fatal myocardial infarction, fatal and non-fatal stroke, hospitalization for heart failure, cardiovascular death, the composite of cardiovascular death or hospitalization for heart failure, the renal composite, and all-cause mortality) will be analyzed using Cox proportional hazards models with the same model terms as those included for the primary endpoint. A point estimate and two-sided nominal 95% confidence interval for the hazard ratio will be calculated based on the Cox model for

090177e187d04317\Approved\Approved On: 14-Mar-2016 14:12

each endpoint. Kaplan-Meier methodology will be used to estimate event rates over time for each treatment group.

If non-inferiority at the 1.3 margin is established for the primary MACE endpoint based solely on this study, then tests of superiority on the secondary endpoints of cardiovascular death or hospitalization for heart failure (composite), cardiovascular death (individual component), and the renal composite will also be performed. The population for superiority testing will include all randomized subjects and include all confirmed events, including those occurring more than 365 days following discontinuation of investigational product. Superiority tests will be implemented by comparing the upper bound of the appropriate alpha-adjusted two-sided CI to 1.0.

In order to control the Type I error rate across multiple hypotheses in Stage 2, a four-step hierarchical testing sequence for the pooled ertugliflozin group versus the placebo group will be utilized as follows:

1. Non-inferiority for MACE;
2. Superiority for cardiovascular death or hospitalization for heart failure (composite);
3. Superiority for cardiovascular death (individual component);
4. Superiority for composite of renal death, renal dialysis/transplant, or $\geq 2x$ increase in baseline serum creatinine.

If the result of the test at any step of the sequence is not statistically significant, then testing will stop so that tests further down in the sequence will not be conducted, and the corresponding null hypotheses will not be rejected. The alpha spending to be utilized for the interim and final analyses of the primary and secondary endpoints is described in [Section 9.7](#).

Recurrent MACE and recurrent cardiovascular death or hospitalization for heart failure will also be analyzed using Anderson-Gill models. A point estimate and two-sided 95% confidence interval for the risk ratio (ertugliflozin compared to placebo) will be calculated based on the model for each endpoint. These analyses of recurrent events will be considered exploratory and only performed at the end of the study.

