Once the 1.8 threshold has been met, the study will continue to Stage 2. An interim analysis will take place when approximately 714 MACE events have accrued in this study. The purpose of this analysis will be to rule out an HR of 1.3 for MACE and to sequentially test for superiority on the secondary endpoints of cardiovascular death or hospitalization for heart failure (composite), cardiovascular death (individual component), and the renal composite. If necessary (ie, if the interim analysis fails to rule out an HR >1.3 or to achieve superiority on both of the secondary CV endpoints), the final analysis will take place after accrual of approximately 939 MACE events. For the primary non-inferiority analysis of MACE, the two-sided adjusted CI for the HR will be calculated using an O'Brien-Fleming spending function to preserve the overall Type I error rate of 2.5% with respect to the non-inferiority margin of 1.3. The analysis at approximately 714 MACE events corresponds to an information fraction of approximately 76%, and the amount of alpha to be spent for this analysis is about 1.0% (one-sided). The subsequent secondary hypothesis tests will utilize a similar O'Brien-Fleming alpha spending approach with a 2.0% two-sided alpha spend for each hypothesis at the interim. If at the end of the study, the upper bound of the two-sided adjusted CI is <1.3 for MACE, the study will be considered to have met its primary objective of demonstrating the non-inferiority of ertugliflozin as compared to placebo with respect to cardiovascular safety. Details regarding alpha spending and power for the primary analyses at each potential analysis time are described in Table 6 below.

Table 6. Alpha Adjusted Confidence Interval and Power for Primary Analyses

Stage	Analysis (within Stage)	Events (confirmed by adjudication)	Alpha for adjusted confidence interval (one-sided)	Power to Demonstrate Non-Inferiority*
1 Phase 2 and 3 Meta-analysis	1 Interim	130 MACE plus	1.0%	79.5%
	If the upper bound at interim analysis is ≥ 1.8 for MACE plus			
	2 Final	173 MACE plus	2.2%	95.1% (cumulative)
Once the 1.8 threshold has been met, the study will continue to Stage 2				
2 Study P004/B1521021	1 Interim	714 MACE	1.0%	83.8%
	If the upper bound at interim analysis is ≥ 1.3 for MACE			
	2 Final	939 MACE	2.2%	96.4% (cumulative)

* Power under HR=1.0

090177e187d04317\Approved\Approved On: 14-Mar-2016 14:12

Interim Futility Analysis for Secondary Endpoints

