The overall Type I error rate in Stage 2 will be strongly controlled using a combination of fixed sequential testing across endpoints and alpha spending approaches across analysis time points.^{17,18} The following chart summarizes the alpha levels that will be utilized for each endpoint at each analysis time point in Stage 2. The fixed sequential testing sequence of the endpoints is described in [Section 9.3](#). Note that alpha allocated to the secondary superiority tests at the interim will be considered to be consumed even if the test is not conducted due to the hierarchical testing sequence. Also note that if the primary non-inferiority test is successful at the interim, but the study continues to the final analysis for the secondary superiority tests, a supportive analysis of the primary non-inferiority hypothesis will be conducted at the final analysis time point using the full alpha level of 0.025. Similarly, if the secondary superiority test for the composite of CV death and hospitalization for heart failure is successful at the interim but the study continues to the final analysis (ie, the secondary superiority test for CV death is not successful at the interim), a supportive analysis of the secondary superiority hypothesis for CV death and hospitalization for heart failure will be conducted at the final analysis time point using the full alpha level of 0.05.

090177e187d04317\Approved\Approved On: 14-Mar-2016 14:12

Sequence Number*	Endpoint (test)	Alpha for adjusted confidence interval	
		Interim Analysis	Final Analysis
1	MACE (non-inferiority)	1% (one-sided)	2.2% (one-sided); if test not successful at interim
			2.5% (one-sided); if test successful at interim
2	Cardiovascular death/hospitalization for heart failure (superiority)	2% (two-sided)	4.4% (two-sided); if test not successful at interim
			5% (two-sided); if test successful at interim
3	CV death (superiority)	2% (two-sided)	4.4% (two-sided)
4	Renal composite (superiority)	2% (two-sided)	4.4% (two-sided)

*Note: If the result of the test at any step of the sequence is not statistically significant, then testing will stop so that tests further down in the sequence will not be conducted (and therefore not considered successful).

The various possible actions to be taken based on the Stage 2 interim analysis results are summarized in the following table:

Scenario at Interim	Action
Primary test unsuccessful	Study continues to final analysis

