**Table 2. TRS-HFDM in the Derivation Cohort**

Risk Indicator	Adjusted HR (95% CI)	P Value	Points
Prior heart failure	4.22 (3.18–5.59)	<0.001	2
Atrial fibrillation	2.26 (1.62–3.14)	<0.001	1
Coronary artery disease	2.06 (1.45–2.93)	<0.001	1
eGFR <60 mL·min  ·1.73 m 	1.85 (1.40–2.46)	<0.001	1
Urine albumin-to-creatinine ratio			
>300 mg/g	4.50 (3.18–6.36)	<0.001	2
30–300 mg/g	2.08 (1.50–2.87)	<0.001	1

eGFR <60 mL·min·1.73 m^-2 represents chronic kidney disease. Urine albumin-to-creatinine ratio 30–300 mg/g represents moderately increased albuminuria, whereas >300 mg/g represents severely increased albuminuria. eGFR indicates estimated glomerular filtration rate; HR, hazard ratio; TIMI, Thrombolysis in Myocardial Infarction; and TRS-HFDM, TIMI Risk Score for Heart Failure in Diabetes.

Berg et al

Heart Failure Risk Stratification in Diabetes

**Figure 2. Treatment effect of dapagliflozin by baseline risk of hospitalization for heart failure.** Although relative risk reductions were similar across risk score categories, absolute reductions in Kaplan-Meier estimates of hospitalization for heart failure risk at 4 years were greater in those at higher baseline risk ( $\chi^2=3.24$ ; 1-sided P for trend=0.04). ARR indicates absolute risk reduction; HR, hazard ratio; and NNT, number needed to treat.

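### The superiority Cox models for CV death/HHF and CV death adjust for no baseline predictor; adding those already collected would gain roughly 0.5 to 1.5 points of power

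*Protocol*

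**What the plan says.** Protocol 9.2 states that MACE plus and MACE "will be analyzed using a stratified Cox proportional hazards model including treatment group as a covariate". For Stage 2 the only stratification factor is Cohort, with two levels set by randomization date. Protocol 9.3 then says that the secondary time-to-event endpoints "will be analyzed using Cox proportional hazards models with the same model terms as those included for the primary endpoint". CV death/HHF and CV death, steps 2 and 3 of the four-step testing sequence, are on that list. The Stage 2 table in SAP Appendix 2 gives the method for both as a Cox proportional hazards model and mentions no covariates.

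For the formal tests, Protocol 9.7 sets a "2.0% two-sided alpha spend for each hypothesis at the interim" and, for CV death/HHF at the final analysis, "4.4% (two-sided); if test not successful at interim". Protocol 9.1 assumes "at least 442 and 582 composite events of cardiovascular death or hospitalization for heart failure at the interim and final analysis respectively", with a true hazard ratio of 0.75 and about 90% power. For CV death it assumes 287 and 377 events, a hazard ratio of 0.725 and about 83% power.

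Prognostic terms do appear in the SAP supplement (region, type of vascular disease, prior MI, prior stroke, history of heart failure), but only in the supportive and exploratory models of its Sections 2 and 3.

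**The concern.** The trial already holds baseline variables that should predict these endpoints. SAP Appendix 2 reports CAD for every subject (1,990 no + 6,256 yes = 8,246), albuminuria category for all but 243 (2.9%), and prior heart failure for the full 8,246. SAP Appendix 1 reprints a heart failure risk score in which the hazard ratios for HHF are 4.22 for prior heart failure, 2.06 for CAD, and 2.08 and 4.50 for albuminuria of 30–300 and above 300 mg/g.

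In a Cox model, leaving out a strong predictor yields a treatment log hazard ratio nearer zero than the within-risk-group one, with almost the same standard error, so the test statistic is smaller on average. What is at stake is some power on the first superiority test. Because the sequence stops at the first failure, a miss there also blocks CV death and the renal composite. The plan does accept baseline covariates elsewhere: the glycemic sub-study models in Protocol 9.8 include baseline eGFR.

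**Working it through.** **Step 1: reproduce the stated powers.** With the doses pooled, allocation is 2:1, so with d events the expected test statistic is E[Z] = |ln HR| × √(d × 1/3 × 2/3). The nominal two-sided levels of 2.0% and 4.4% give critical values of 2.326 at the interim and 2.014 at the final analysis.

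- CV death/HHF, interim: 0.2877 × √(442 × 2/9) = 2.851, and Φ(2.851 − 2.326) = 70.0%. Protocol 9.1 says about 70%.
- CV death/HHF, final: 0.2877 × √(582 × 2/9) = 3.272, and Φ(3.272 − 2.014) = 89.6% for the final look alone. Over both looks (bivariate normal, correlation √(442/582) = 0.871), power is 90.0%.
- CV death, final: 0.3216 × √(377 × 2/9) = 2.943, and Φ(2.943 − 2.014) = 82.4%. Over both looks, power is 83.1%.

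The stated 90% and 83% are therefore reproduced.

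**Step 2: simulate the effect of adjustment.** Each trial had 8,000 subjects in two cohorts, 5% per year withdrawal and 6.1 years of study time, with the event rate set to give about 582 or 377 events. Baseline prevalences were those of SAP Appendix 2: prior heart failure 23.4%, CAD 75.9%, albuminuria 30.1% (middle category) and 9.1% (top category). The predictors were simulated as independent. Each scenario used 5,000 trials, each fitted with a cohort-stratified Cox model with and without the predictors. The risk-score hazard ratios were used at full strength and with their logs multiplied by 0.75 and 0.5. Let k be the mean Z of the adjusted model divided by that of the unadjusted model.

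**Step 3: return k to the two-look calculation.** If the protocol's hazard ratio is marginal, the adjusted model works at HR^k. If it is conditional, the unadjusted model works at HR^(1/k). Results for prior heart failure, CAD and albuminuria together:

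| Endpoint | Strength | k | Power if HR is marginal | Power if HR is conditional | Difference (points) |
|---|---|---|---|---|---|
| CV death/HHF | full | 1.054 | 90.0% → 92.8% | 86.8% → 90.0% | 2.7 to 3.2 |
| CV death/HHF | 0.75 | 1.026 | 90.0% → 91.4% | 88.5% → 90.0% | 1.4 to 1.5 |
| CV death/HHF | 0.5 | 1.010 | 90.0% → 90.6% | 89.5% → 90.0% | 0.5 |
| CV death | full | 1.035 | 83.1% → 85.5% | 80.4% → 83.1% | 2.5 to 2.6 |
| CV death | 0.75 | 1.017 | 83.1% → 84.3% | 81.8% → 83.1% | 1.2 |
| CV death | 0.5 | 1.006 | 83.1% → 83.5% | 82.6% → 83.1% | 0.45 |

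For CV death/HHF, the equivalent in extra events is 582 × (k² − 1), from unrounded k: about 64 at full strength, 30 at 0.75 and 11 at 0.5.

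Prior heart failure alone at full strength is worth 1.4 to 1.5 points for CV death/HHF and 1.2 for CV death. A separate run with 400 replicates per scenario gave k = 1.014 at 60% strength and 1.011 at 50%, or about 0.6 to 0.7 point. Adding eGFR below 60 and atrial fibrillation, at assumed prevalences of 22% and 9%, gives 3.3 to 4.1 points for CV death/HHF at full strength, 1.7 to 1.9 at 0.75 and about 0.65 at half. Those figures are not relied on, because the prevalences are assumed.

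**The case against.** The strongest reply is that nothing is wrong. A cohort-stratified Cox test in all randomized subjects holds its alpha, and the planned powers follow from it. That stands. A reader might infer that the planned estimate is biased toward 1 or that the 90% and 83% are overstated. The documents support neither. Protocol 9.1 says only that the true hazard ratio is 0.75 or 0.725. If these are marginal values, which is what the planned model estimates, power is as stated. The adjusted hazard ratio is a different, conditional quantity.

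A reader might also take 3 points as the expected loss. It is not. The hazard ratios in SAP Appendix 1 are for HHF, come from another trial's derivation cohort, and are listed under future analyses. The documents give none for CV death or for the composite, and with 377 CV deaths planned against 582 composite events, up to about 65% of composite events (377/582) may be CV deaths. The CAD ratio may also transfer poorly, since every subject here without CAD qualifies through cerebral or peripheral disease. Independent predictors and a correctly specified fitted model favour adjustment as well.

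Extending the point to the renal composite is tempting, but no gain was computed for it.

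Finally, the supplement already plans some adjusted Cox models, and the full primary SAP is not among the documents, so adjusted sensitivity analyses may exist there. The excerpts in SAP Appendix 2 show none, and the supplement's own adjusted models lie outside the testing sequence.

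**Conclusion.** The point holds as a modest efficiency gain, not a defect. The formal Cox models for CV death/HHF and CV death carry only treatment and cohort. Adjusting for prior heart failure, CAD and albuminuria category would raise power by roughly 0.5 to 1.5 points if the predictors act at half to three quarters of the reprinted strength on the log scale. About 3 points is the ceiling for these three predictors. The size rests on an assumed predictor strength for these endpoints and on independence of the predictors. The gain comes from a log hazard ratio further from zero, not from a smaller standard error.

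**What to change.** Before any unblinded Stage 2 analysis, and identically at interim and final, specify the Cox models for CV death/HHF and CV death with cohort as stratum and these terms besides treatment:

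- prior heart failure (yes/no) under one stated definition, for example the narrow Cardiac Failure SMQ applied to medical history. SAP Section 2 gives 1,900/8,238 and the Appendix 2 table 1,933/8,246, so the source must be fixed;
- CAD (yes/no);
- baseline albuminuria category, with a level for missing;
- optionally, baseline eGFR.

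Ejection fraction is a poor choice, because it is missing in about 39% of subjects (5,005 of 8,246 have a value). Report the cohort-only model as a sensitivity analysis.

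The change needs no new data, subjects or alpha. It has two costs. The hazard ratio becomes conditional and must be labelled so. And because the model is written into Protocol 9.2 and 9.3, and Section 9 requires major changes to the analyses to be reflected in a protocol amendment, an amendment may be needed rather than SAP wording alone. The documents do not say whether the Stage 2 interim has been run. If it has, the formal tests should keep the cohort-only model, and the adjusted model can only be supportive.
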